10. STATISTICAL CONSIDERATIONS

Sample Size and Power Analysis: We will estimate the signal-to-noise ratio (SNR) at the sensor level, which will allow us to calculate the intra-subject variability. Given this SNR, we anticipate an effect size (Cohen's *d*) of greater than 0.5 in the primary motor cortex (M1). For an effect size of 0.5, 15 subjects per group are required to achieve 80% power at a significance level of 0.05. This estimation assumes a moderate effect of 6-Hz primed rTMS on motor function and meta-plasticity outcomes.

Handling Missing Data: Given the possibility of dropouts or incomplete data, particularly in a pediatric population, multiple imputation methods will be employed to handle missing data. We will also conduct sensitivity analyses to assess the impact of missing data on the results, ensuring robustness in our findings.

Multiple Comparisons and Adjustment: Considering the multiple outcome measures related to motor function, cortical excitability, and meta-plasticity, we will apply False Discovery Rate (FDR) adjustments to control for Type I error. This approach balances the need to maintain statistical rigor while not being overly conservative, which is crucial given the exploratory nature of some of our outcomes.

Effect Size and Clinical Relevance: While statistical significance will be assessed using *p*-values, we will also report effect sizes (Cohen's *d*) to gauge the practical relevance of our findings. An effect size greater than 0.5, particularly in motor outcomes, will be considered clinically meaningful, contributing to the broader understanding of rTMS effects in pediatric CP.

Controlling for Confounding Variables: Behavioral scores, laterality, age, and gender will be included as covariates in our analysis to control for their potential confounding effects. We will employ Analysis of Covariance (ANCOVA) models to adjust for these variables, ensuring that the observed effects are attributable to the rTMS intervention rather than these extraneous factors.

Longitudinal Data Analysis: Given the repeated measures design, where participants will be assessed at multiple time points, we will use mixed-effects models to account for within-subject correlations. This approach will allow us to capture the temporal dynamics of rTMS effects on motor function and meta-plasticity accurately, providing a more comprehensive understanding of the intervention's impact over time.

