3. STUDY DESIGN

3.1 Type/Design of Trial

This study will be a randomized, double-blind, sham-controlled trial designed to assess the efficacy of 6-Hz primed low-frequency rTMS applied to the ipsilesional hemisphere and 6-Hz primed high-frequency rTMS administered to the contralesional hemisphere on improving motor function and meta-plasticity in children with CP. We will recruit 45 children with CP (6-18 years old) to test this along with 15 TD kids to compare the TEPs of them with CP children (with no intervention). The CP children will be randomly assigned to experimental group 1, experimental group 2, and a sham group (15 children in each group). The study design is shown in [Figure 1](#). TD children's participation is limited to non-interventional assessments for TEPs comparison purposes only (~3 hours). They will not receive any rTMS intervention. All the assessments and training will be done in the TMS room in the Dodson building. Behavioral assessment will be done at baseline, Day 12 post-intervention, and follow-up within one month. A session of the assessment will be completed in ~3 hours. Each assessment session can be separated into two successive days if a child and/or the parent/guardian do not want to complete the session one time.

[figure not shown]

Figure 1: Flow chart diagram of the study's design.

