10.1 Treatment Assignment Procedures

10.1.1 Behavioral Scores Statistical Analysis

Nonparametric Mann-Whitney U tests will examine relationships between continuous and categorical data. Spearman correlation will be used to evaluate the relationships between the behavioral ratings and the HD-EEG measures. Depending on the tests conducted, distinct univariate linear regressions will be carried out to assess the slope of the association between HD-EEG and behavioral scores. After that, multivariate general linear regression will be carried out for the candidate variables connected to the results of each behavioral test. Two-tailed $\alpha < 0.05$ will be used in all tests.

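### Fifteen children per group do not give 80% power at Cohen's d = 0.5: the stated inputs give about 26% unadjusted, and 80% needs 64 per group

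*Protocol*

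**What the plan says.** The sizing statement is in Protocol section 10, under Sample Size and Power Analysis: "For an effect size of 0.5, 15 subjects per group are required to achieve 80% power at a significance level of 0.05". The measure is named in the sentence before it: "Given this SNR, we anticipate an effect size (Cohen's *d*) of greater than 0.5 in the primary motor cortex (M1". The signal-to-noise ratio on which this rests is described there as something still to be estimated. The paragraph calls the assumed effect moderate and applies it to both motor function and meta-plasticity outcomes.

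The other inputs are elsewhere in the Protocol:

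- Section 3.1 allocates 45 children with CP to "experimental group 1, experimental group 2, and a sham group (15 children in each group").
- Section 2.2 makes the primary objectives a comparison of low- with high-frequency primed rTMS, which is a comparison between independent groups. Section 10.1.2 item f adds comparisons with sham.
- Section 10.1.1: "Two-tailed $\alpha < 0.05$ will be used in all tests".
- Section 10, on clinical relevance: "An effect size greater than 0.5, particularly in motor outcomes, will be considered clinically meaningful".

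Section 10 also plans ANCOVA, mixed-effects models, FDR adjustment and multiple imputation. The sizing statement uses none of them. It gives no correlation, no dropout rate and no named test.

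**The concern.** For a two-group comparison at d = 0.5, a statistician expects a requirement of just over 60 per group. Fifteen is about a quarter of that. The figure is printed in the Protocol as a result, so it is not a detail left to a later analysis plan.

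The design effect is also the effect the Protocol calls clinically meaningful. If power at that size is far below 80%, a non-significant comparison cannot be taken to show that a meaningful effect is absent, yet a reader who trusts the stated power could take it that way.

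**Working it through.** **Inputs.** d = 0.5 (already standardised, so SD = 1), n = 15 per group, α = 0.05 two-sided, two independent groups. All come from the sections listed above.

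**1. The plan's own figure.** Two-sample t test:

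- Degrees of freedom: 2 × 15 − 2 = 28; critical t = 2.048.
- Noncentrality: d × √(n/2) = 0.5 × √7.5 = 1.369.
- Power from the noncentral t: **26.2%** (27.7% by the normal approximation). The stated 80% is not reproduced.
- Size for 80%: 63 per group gives 79.5% and **64** gives 80.1%, so 3 × 64 = 192 children against 45.
- Effect detectable with 80% power at 15 per group: **d = 1.06**.

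**2. Other readings that keep d = 0.5.**

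| Reading | Power at the planned size |
|---|---|
| One-sided two-sample t (contrary to section 10.1.1) | 37.9% |
| Mann-Whitney, approximate | 25% |
| Both active groups pooled (30) against sham (15) | 34.0% |
| Within one group, paired, n = 15 (does not answer section 2.2) | 43.8% |
| Three-group ANOVA, largest pairwise d = 0.5 | 20–26% |

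**3. Credit for baseline adjustment.** If d is in raw SD units and the baseline/follow-up correlation is ρ, ANCOVA acts on d/√(1 − ρ²). The Protocol gives no ρ, so these values are assumptions:

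| ρ | Effective d | Power, 15 per group |
|---|---|---|
| 0.5 | 0.577 | 33% |
| 0.7 | 0.700 | 46% |
| 0.8 | 0.833 | 60% |
| 0.9 | 1.147 | 86% |

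For 80% the effective d must be 1.06, so ρ = √(1 − (0.5/1.06)²) = **0.88**. A change-score analysis needs about 0.89.

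**4. What does reproduce about 15 per group.**

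- *Cohen's f = 0.5, three-group one-way ANOVA*: 80.3% at N = 42 (14 per group), 83.4% at N = 45. With three equally spaced means over a range R, f = 0.408R, so R = 0.5/0.408 = 1.22. With two means equal and one apart, f = 0.471R, so R = 1.06. The largest pairwise d is then about 1.06 to 1.22.
- *Group-by-time f = 0.25, two time points, correlation 0.5*: N = 42 for 80%, and 83% at N = 45. With two groups and two time points the interaction effects are ± one quarter of the difference in change, so f = 0.25 means a difference in change of 4 × 0.25 = 1 SD.

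Both need inputs the Protocol does not state, and both correspond to about 1 SD.

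**5. What a null result could exclude.** The half-width of an unadjusted 95% interval for a two-group difference is about 2.048 × √(2/15) = 0.75 SD. An estimate of zero would leave d = 0.5 well inside the interval.

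**6. Factors that lower power.** Section 10 expects dropouts and plans FDR adjustment, but gives no rate and no fixed threshold. As illustrations only: 12 completers per group gives 22%, and a test at 0.025 gives 18%.

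**The case against.** The strongest reply is that 26% describes an analysis the Protocol does not plan to rely on. Section 10 specifies ANCOVA with behavioural scores as covariates, and mixed models for repeated assessments. A group-by-time test at f = 0.25, conventionally a medium effect, with correlation 0.5 gives 83% at 45 children. On that view the number 15 may have come from a legitimate calculation that was badly described.

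Part of this stands. The power of the planned analysis is a range that depends on an unstated correlation, so a reader who inferred that the trial's true power is 26% would go too far. A reader might also infer that no recognised calculation yields 15 per group; step 4 shows two that do. Nor does the Protocol show that d and f were confused. That is one possible origin and remains conjecture.

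The reply does not rescue the sentence. It names d, claims no adjustment and gives no correlation. The calculations that match assume effects of about 1 SD, roughly twice the stated d. A correlation of 0.88 might be argued for GMFM-88, but it would have to be stated, and it would have to hold for TEPs too, because the sizing paragraph covers both kinds of outcome.

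A last tempting inference is that a null result would be uninformative. It would still bear on large effects, since d near 1.06 is detectable with 80% power. What it could not do is rule out d = 0.5.

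**Conclusion.** The power statement is wrong as written and must be corrected. From the Protocol's own inputs, power is about 26% against the stated 80%, and the size needed is 64 per group against 15. These figures are for an unadjusted, two-sided, two-group comparison with all 15 per group analysed.

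Under the planned ANCOVA, power at d = 0.5 is about 33% to 60% for assumed correlations of 0.5 to 0.8, and reaches 80% only near 0.88. Dropout and multiplicity adjustment would pull it down by amounts the Protocol does not allow to be fixed.

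The consequence is limited but important: a non-significant result could not exclude the effect size the Protocol itself calls clinically meaningful. The basis for the effect size is also unsupported, because it is said to follow from a signal-to-noise ratio that has yet to be estimated.

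**What to change.** Without changing the 45 children, replace the sizing sentence in section 10 with wording such as: *15 per group gives 80% power to detect d = 1.06 (two-sided 0.05, unadjusted two-group comparison); power at d = 0.5 is about 26%.*

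If credit is taken for baseline adjustment or repeated measures, state the test, the effect measure (d or f, and in which SD units) and the assumed correlation with its source, and give the power that follows for each primary outcome. Give a source for the effect size, or remove its derivation from the signal-to-noise ratio.

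The cost is a wording amendment that makes the stated figure less favourable. It needs no extra participants and no change to procedures. Should the sponsor prefer to keep 80% power at d = 0.5 without adjustment, the alternative is 64 per group (192 children) before any allowance for dropout.

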10.1 Treatment Assignment Procedures

10.1.1 Behavioral Scores Statistical Analysis

Nonparametric Mann-Whitney U tests will examine relationships between continuous and categorical data. Spearman correlation will be used to evaluate the relationships between the behavioral ratings and the HD-EEG measures. Depending on the tests conducted, distinct univariate linear regressions will be carried out to assess the slope of the association between HD-EEG and behavioral scores. After that, multivariate general linear regression will be carried out for the candidate variables connected to the results of each behavioral test. Two-tailed $\alpha < 0.05$ will be used in all tests.

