- e. Source Localization:** Source localization techniques, such as Minimum Norm Estimates (MNE), will be employed to estimate the neural sources of the observed EEG activity. This step also involves functional connectivity analysis to explore changes in connectivity between different brain regions, particularly those involved in motor functions and meta-plasticity.
- f. Statistical Analysis:** Statistical analysis compares EEG data between different stimulation conditions (low vs. high-frequency rTMS) and sham. Correlations between EEG findings and behavioral outcomes will be examined to understand the relationship between brain activity and motor function or meta-plasticity. Covariates such as age, gender, and behavioral scores will be included in statistical models to isolate the effects of rTMS.

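### The EEG-behavior associations are specified without age adjustment in children aged 6 to 18, and the age covariates named elsewhere are not clearly carried to them.

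*Protocol*

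**What the plan says.** Protocol section 10.1.1 sets out three steps for the EEG-behavior question.

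- Rank correlation: "Spearman correlation will be used to evaluate the relationships between the behavioral ratings and the HD-EEG measures".
- Separate regressions: "distinct univariate linear regressions will be carried out to assess the slope of the association between HD-EEG and behavioral scores".
- A joint model: "After that, multivariate general linear regression will be carried out for the candidate variables connected to the results of each behavioral test".

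None of the three names age. Section 10.1.2, step f, returns to the subject without a method: "Correlations between EEG findings and behavioral outcomes will be examined to understand the relationship between brain activity and motor function or meta-plasticity".

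Age does appear as a covariate in two places. Section 10, under Controlling for Confounding Variables, says "Behavioral scores, laterality, age, and gender will be included as covariates in our analysis to control for their potential confounding effects". It assigns this to ANCOVA models, with the purpose of "ensuring that the observed effects are attributable to the rTMS intervention rather than these extraneous factors". In section 10.1.2, step f, the sentence after the one on correlations reads "Covariates such as age, gender, and behavioral scores will be included in statistical models to isolate the effects of rTMS".

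Section 3.1 gives the population: 45 children with CP aged 6 to 18, and 15 typically developing children seen once.

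**The concern.** Over a 12-year age span, a motor score and an EEG measure can each move with age. A rank correlation or one-predictor slope then shows an association even if, among children of the same age, the two are unrelated. A marker of maturation could be reported as a marker of motor function or meta-plasticity.

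The protocol itself gives reason to expect age dependence in some behavioral measures. Section 1.1 notes that mirror movements are common in early typical development, and the MMAS rates them. Section 6.1.1.2 describes GMFM-88 through raw and percentage scores and mentions no age norms. Section 6.1.2.5 scores the hand function test by completion time over the full age range.

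Randomization balances age across arms in expectation, so the treatment comparison has protection of its own. A correlation across children has none, and this is where the age adjustment is not clearly stated.

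**Working it through.** **Does the age adjustment reach this step?** Both covariate sentences, in section 10 and in step f, give the rTMS effect as their purpose. Both also list behavioral scores among the covariates. A model that treats behavior as a nuisance variable is not the model that estimates the EEG-behavior association. A plain Spearman coefficient takes no covariate, and a univariate regression has one predictor by definition. The multivariate step could include age, but the text does not say so. The FDR adjustment in section 10 deals with multiplicity and does not remove confounding.

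**How large could the effect be?** The protocol gives no figure for these associations and no correlation of any measure with age, so there is no stated figure to reproduce.

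Inputs:

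- From the protocol: n = 45, ages 6 to 18, two-sided 5% level.
- Assumed: age uniform on 6 to 18; age correlates at the same value ρ with both measures; no association at a given age; level scores rather than within-child changes.

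With z the standardized age, EEG = ρz + √(1 − ρ²)·e₁ and behavior = ρz + √(1 − ρ²)·e₂, where e₁ and e₂ are independent standard normal. The correlation produced by age alone is ρ × ρ = ρ².

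Age-partial correlation: (r_EB − r_EA·r_BA) / √[(1 − r_EA²)(1 − r_BA²)], computed on ranks and tested on n − 3 degrees of freedom. E, B and A stand for EEG, behavior and age.

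Hand check at ρ = 0.5 by Fisher's transformation, for the Pearson correlation (equivalent to the univariate slope test):

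- ρ² = 0.25, and atanh(0.25) = 0.2554.
- 0.2554 × √(45 − 3) = 0.2554 × 6.481 = 1.655.
- The chance of exceeding 1.960 is Φ(1.655 − 1.960) = Φ(−0.305) ≈ 0.38.

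Simulation, 20,000 runs per row, n = 45:

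| ρ with age (assumed) | Mean Spearman | Plain Spearman significant | Age-partial Spearman significant | Univariate slope significant | Slope with age in model |
|---|---|---|---|---|---|
| 0 | 0.00 | 5.1% | 5.0% | 5.0% | 5.1% |
| 0.3 | 0.09 | 8.9% | 4.9% | 8.8% | 4.8% |
| 0.4 | 0.16 | 17.9% | 5.3% | 18.5% | 4.9% |
| 0.5 | 0.24 | 37.7% | 5.4% | 38.7% | 5.1% |
| 0.6 | 0.36 | 68.9% | 5.6% | 70.8% | 5.2% |

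The simulated 38.7% for the slope at ρ = 0.5 agrees with the hand check.

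The rate depends on n. At ρ = 0.5, plain Spearman is significant in 14.1% of cases with 15 children. It is 48.2% with 60, which would apply only if the typically developing children were pooled with the others; the protocol does not say that they are.

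**The case against.** The strongest reply is that the protocol does recognize age. It names age as a covariate twice, once directly after the sentence on EEG-behavior correlations, and section 10.1.1 does not stop at the plain tests. This stands as far as it goes: a reader might infer that age is ignored throughout, and that is not so. But both statements are directed at the rTMS effect, and the correlation and univariate steps are named in a form that admits no covariate. A SAP could settle the scope, yet the protocol has already fixed the method.

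A reader might also infer that the multivariate regression is restricted to EEG variables that were significant in the unadjusted steps, so that it could not repair them. The text does not say this. It sets no screening rule, does not limit the candidates to EEG variables and does not exclude age.

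Nor is the EEG-behavior link a stated aim of the efficacy comparison. No such association appears among the objectives in sections 2.2 and 2.3 or the outcomes in section 3.2. Section 1.1 speaks only generally of joining behavioral assessment to mechanism.

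Two technical objections also hold. First, plain Spearman is a correctly sized test of marginal association. If both measures follow age, that association exists, and the error lies in reading it as a brain-motor link. Second, the figures depend on the assumed correlations. At 0.3 the excess is about 4 percentage points, and if only one measure moves with age there is none.

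**Conclusion.** The point holds as a gap in the specification of a supportive analysis. As written, the rank correlations and univariate slopes are unadjusted for age, and the multivariate step does not commit to adjusting for it.

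The size is conditional. For level scores, with equal assumed age correlations of 0.3 to 0.6 and no link at a given age, about 9% to 69% of plain Spearman tests at n = 45 would be significant, against about 5% to 6% after partialling out age. The protocol does not say whether baseline, post-treatment or change values are correlated. Within-child changes would be less exposed, so the upper end should not be read as a prediction.

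The randomized treatment comparisons are not affected. A reader might also conclude that arm must be forced into every association model. Neither the documents nor the calculation supports that: the calculation concerns age only, and adjusting for arm removes between-arm covariation that may be part of a treatment-related brain-motor link.

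**What to change.** In section 10.1.1 and section 10.1.2, step f:

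- Make partial Spearman correlation given age the reported EEG-behavior correlation.
- Include age in each EEG-behavior regression, and say explicitly that it enters the multivariate step.
- State whether baseline or change values are used.
- Where post-treatment or change values are pooled across arms, add an arm-adjusted result as a sensitivity analysis.

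The cost is one degree of freedom for age, two for arm in the sensitivity analysis (three groups), and a little more analysis work. Age is already collected (section 5) and arm is known, so no new data are needed.

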- e. Source Localization:** Source localization techniques, such as Minimum Norm Estimates (MNE), will be employed to estimate the neural sources of the observed EEG activity. This step also involves functional connectivity analysis to explore changes in connectivity between different brain regions, particularly those involved in motor functions and meta-plasticity.
- f. Statistical Analysis:** Statistical analysis compares EEG data between different stimulation conditions (low vs. high-frequency rTMS) and sham. Correlations between EEG findings and behavioral outcomes will be examined to understand the relationship between brain activity and motor function or meta-plasticity. Covariates such as age, gender, and behavioral scores will be included in statistical models to isolate the effects of rTMS.

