In the study by Tallabs and Hammond-Tooke (2013), the authors investigated whether theta priming with 6-Hz theta-burst stimulation (TBS) could enhance the inhibitory effects of 1-Hz rTMS on the motor cortex in healthy volunteers. The study design compared three protocols: 10 minutes of 1-Hz rTMS alone, 5 minutes of 6-Hz TBS followed by 5 minutes of 1-Hz rTMS, and a sham condition using a sham coil. The primary outcome measures included changes in resting and active MEP amplitudes and unimanual reaction times. The results showed that 1-Hz rTMS alone significantly reduced resting and active MEP amplitudes, indicating effective corticospinal inhibition. However, when 1-Hz rTMS was preceded by theta priming, this inhibitory effect was abolished, suggesting that the priming protocol interfered with the subsequent inhibitory effects of 1-Hz rTMS. Interestingly, despite the lack of enhanced inhibition, both 1-Hz rTMS protocols significantly reduced reaction times compared to the sham condition with and without theta priming⁴³.

The study by Kakuda et al. (2011) investigates the safety, feasibility, and efficacy of combining 6-Hz primed low-frequency rTMS with intensive occupational therapy (OT) for improving upper limb function in stroke patients. Primed rTMS involves a brief period of high-frequency stimulation (6-Hz) followed by low-frequency rTMS (1-Hz) targeting the non-lesional hemisphere. This approach moderates cortical excitability, reduces IHI, and promotes motor recovery in the affected hemisphere⁴⁴.

Studies have demonstrated that 6-Hz primed low-frequency rTMS can modulate cortical excitability, potentially enhancing motor function in stroke patients⁴⁵. Todd et al. (2009) demonstrated that while priming with 2 or 6-Hz rTMS did not significantly alter the inhibitory effects of continuous theta-burst stimulation (cTBS), priming with iTBS led to more significant suppression of MEPs compared to cTBS alone. This finding suggests that excitatory priming can enhance the inhibitory effects of subsequent cTBS, highlighting the complex interplay between different stimulation protocols in inducing metaplastic changes⁴⁶.

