2.2 Primary Objectives

- 2.2.1 To assess and compare the efficacy of 6-Hz primed low-frequency with 6-Hz primed high-frequency rTMS on motor function in children with CP.

- 2.2.2 To assess and compare the efficacy of 6-Hz primed low-frequency with 6-Hz primed high-frequency rTMS on a meta-plasticity mechanism using TEPs in children with CP.

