3.2 Outcomes

3.2.1 Primary Outcomes Measures

Outcome Measure	Measure Description	Time Frame
Gross Motor Function Measure (GMFM-88)	It is a standardized observational tool specifically created and validated to assess changes in gross motor function over time in children with CP. The GMFM-88 allows for the summation of item scores to generate raw and percentage scores for each of the five GMFM dimensions, the selected goal areas, and an overall GMFM-88 score.	Within the end of 4 weeks and 1-month follow-up of sham/real rTMS
Change on TMS-evoked potentials (TEPs)	TEPs refer to the electrical responses in the brain elicited by rTMS. This technique involves applying magnetic pulses to specific brain areas, which induce electrical activity that can be recorded using EEG.	Within the end of 4 weeks and 1-month follow-up of sham/real rTMS

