3.6.3 HD-EEG Recording

The HD-EEG setup involves placing electrodes across the scalp to monitor brain responses while applying rTMS. We will use a 64-channel system (eego mylab and Waveguard™ cap, ANT Neuro, Enschede, The Netherlands). This allows for precise mapping of the brain's electrical activity, enabling the investigation of changes in motor function and meta-plasticity induced by different rTMS frequencies in children with CP. See 5.1.2 for details of the HD-EEG.

3.6.4 rTMS

CP Participants in Experiment Group 1 will use rTMS using a figure-of-eight-shaped coil and rTMS stimulator (Nexstim, Finland) targeting the contralesional primary motor cortex. The intervention will consist of 10 sessions, each lasting 20 minutes, spread over four weeks. Each session will begin with priming: 10 minutes of 6-Hz rTMS at 90% of the resting motor threshold, delivered in two trains per minute (5 seconds per train with 25-second intervals between trains), totaling 600 priming pulses. This will be followed immediately by 10 minutes of 1-Hz rTMS at 90% of the resting motor threshold, delivered continuously without interruption, totaling 600 low-frequency pulses⁴⁷.

CP Participants in Experiment Group 2 will receive rTMS targeting the ipsilesional primary motor cortex. The intervention will consist of 10 sessions, each lasting 20 minutes, spread over four weeks. Each session will start with priming: 10 minutes of 6-Hz rTMS at 90% of the resting motor threshold, delivered in two trains per minute (5 seconds per train with 25-second intervals between trains), totaling 600 priming pulses⁴⁷. This will be followed immediately by 10 minutes of 10 Hz rTMS at 90% of the resting motor threshold, delivered continuously without interruption, totaling 2000 high-frequency pulses⁴⁸.

CP Participants in the Sham Group will receive rTMS by positioning the coil perpendicular to the scalp without delivering active stimulation, targeting both the contralesional and ipsilesional primary motor cortex. The intervention will consist of 10 sessions, each lasting 20 minutes, spread over four weeks. Each session will be divided into two parts:

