The Nexstim system utilizes a combination of MRI-based neuronavigation ([Figure 2](#)) and an integrated head tracker ([Figure 3](#)) to map the brain's anatomy and guide the rTMS coil to the exact locations required for effective intervention. The head tracker, a critical component of the Nexstim system, continuously monitors the position and orientation of the TMS coil relative to the child's head, ensuring that the stimulation is delivered consistently and accurately according to the pre-defined parameters.

[figure not shown]

Figure 2: Real-time neuro-navigation using the Nexstim system ensuring accurate coil positioning

The Nexstim NBS 5 system integrates a single pulse coil with the Nexspeech 1.1.2 software for real-time adjustments and monitoring during stimulation. The analyzer 1.1.2 will be

employed to assess the effectiveness of the rTMS and adjust stimulation protocols as needed based on the ongoing data collected from both the rTMS and HD-EEG recordings.

Figure 3: Head tracker on child's head to coregister anatomy with the TMS coil location.

By leveraging these advanced technologies, we aim to enhance the precision of our rTMS interventions and improve the reliability of our findings to motor cortex excitability and brain network modulation.

After the brain mapping is completed, the intervention will use rTMS while the HD-EEG cap remains on the child's head to record TEPs (**Figure 4**). This approach allows for the simultaneous recording of both the cortical responses to rTMS and the ongoing brain activity captured by the HD-EEG, providing a comprehensive view of the neurophysiological effects of the stimulation.

Figure 4: The child sits comfortably in an armchair during the rTMS session. The operator places the electromagnetic coil next to the child's head to stimulate the brain.

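### No common probed hemisphere is fixed for the primary TEP outcome, so a low-versus-high contrast built on treatment pulses cannot separate protocol from side

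*Protocol*

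**What the plan says.** - **Objective.** Protocol 2.2.2 is "To assess and compare the efficacy of 6-Hz primed low-frequency with 6-Hz primed high-frequency rTMS on a meta-plasticity mechanism using TEPs in children with CP".
- **Outcome.** Section 3.2.1 lists "Change on TMS-evoked potentials (TEPs") as a primary outcome and explains that "TEPs refer to the electrical responses in the brain elicited by rTMS". It names no stimulated hemisphere.
- **Recording.** Section 5.1.3 says that, after mapping, "the intervention will use rTMS while the HD-EEG cap remains on the child's head to record TEPs". Section 10.1.2, step b, cuts the epochs around rTMS pulses.
- **Treated side.** In section 3.6.4 the low-frequency arm (Group 1) is treated over contralesional M1. For the other active arm, "CP Participants in Experiment Group 2 will receive rTMS targeting the ipsilesional primary motor cortex". The sham coil is held perpendicular to the scalp over both sides in turn and delivers no active stimulation. Sections 2.1 and 3.1 give the two frequencies the reverse sides. Under either version the active arms are on opposite hemispheres.
- **Comparison.** Section 10.1.2, step f: "Statistical analysis compares EEG data between different stimulation conditions (low vs. high-frequency rTMS) and sham". No hemisphere is specified.
- **Model.** Section 10 plans mixed-effects models over time, with behavioral scores, laterality, age and gender as covariates. Neither baseline TEP nor probed side is listed.

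**The concern.** Followed literally, the protocol takes the TEP from the treatment pulses at the treated site and then compares arms. Each active arm's TEP would come from a different hemisphere and from pulses at a different rate. A difference between low and high frequency could then reflect the protocol, the hemisphere or the pulse rate, and nothing in the data would tell them apart. The laterality covariate does not help: if it meant the stimulated side, it would be collinear with active arm.

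Sham would have no usable counterpart, because pulses without active stimulation evoke no comparable response.

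This cannot be left to a later analysis plan. Which hemisphere is probed is a matter of data acquisition, and a side that was never recorded cannot be recovered. A primary objective is at stake.

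**Working it through.** **1. Passages side by side (reading: outcome TEPs come from treatment pulses).**

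| | Low frequency | High frequency | Sham |
|---|---|---|---|
| Side (3.6.4) | contralesional M1 | ipsilesional M1 | both, half a session each |
| Rate after 6-Hz priming | 1 Hz | 10 Hz | 1 Hz, then 10 Hz, not active |
| Comparable evoked response | yes | yes | no |

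Arm, side and rate move together in the two active columns. On rate alone, pulses are 1/1 s = 1000 ms apart at 1 Hz and 1/10 s = 100 ms apart at 10 Hz. Step b measures components up to P180 and N280. Reading those labels as nominal latencies in milliseconds, these two would fall after the next 10-Hz pulse.

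**2. What the plan gives for size.** Nothing on side differences in TEP. From the plan I take only 15 per arm and two-sided 0.05. Its own power statement (d = 0.5, 80% power, 15 per group) does not reproduce with a two-sample t-test, which needs 64 per group. That is a separate matter and nothing here rests on it.

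**3. Constant side offset, equal efficacy.** Assume the two sides differ by h SD throughout and both protocols have the same additive effect. For raw values the rejection rate is P(|T| > 2.048), with T noncentral t on 28 df and noncentrality h × √(15/2) = 2.739h. At h = 0.5 the noncentrality is 1.369, giving 26%; at h = 1.0 it is 2.739, giving 75%. Change and ANCOVA columns come from 8,000 simulated trials per setting, with baseline correlation ρ.

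| h (SD, assumed) | Raw values | Change from same-side baseline | ANCOVA, ρ = 0.5 | ANCOVA, ρ = 0.8 |
|---|---|---|---|---|
| 0.5 | 26% | about 5% | 11% | 7% |
| 0.8 | 56% | about 5% | 21% | 10% |
| 1.0 | 75% | about 5% | 27% | 12% |
| 1.5 | 98% | about 5% | 44% | 18% |

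A change score removes a constant offset. Adjusting for baseline by ANCOVA removes it only in part.

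**4. Side-specific responses, equal efficacy.** Assume that success lowers the treated-side TEP by d in the low-frequency arm and raises it by d in the high-frequency arm, in SD units of change. The treated-side contrast is then d − (−d) = 2d, and change scores do not remove it. Simulated rejection rates (20,000 trials each) are 18% at d = 0.2, 35% at 0.3, 75% at 0.5 and 99% at 0.8. If both arms are measured on the same hemisphere and respond equally there, the rate is 5% at every d.

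**5. Is opposite sign plausible?** Section 1.2 says of primed low-frequency rTMS to the non-lesional hemisphere in stroke that it "reduces IHI, and promotes motor recovery in the affected hemisphere", which fits success by a route other than exciting the treated side. But section 1.2 also reports a healthy-volunteer study, measuring MEPs and not TEPs, in which theta priming abolished the inhibition produced by 1 Hz. Group 1 receives primed 1 Hz. The sign of its TEP response is therefore not known from the documents, and step 4 is illustration only.

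**The case against.** The best case against runs as follows.

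- **Assessment TEPs may not come from treatment pulses.** Post-intervention and follow-up visits are separate from the 10 treatment sessions (section 5). Section 3.6.4 refers to a pre-intervention TMS-EEG in the CP cohort and describes the similar session in typically developing children as single-pulse. Section 5.1.3 maps each hemisphere, and the EEG covers the whole scalp. This stands: the probed side at assessments is unstated, not stated as opposite. It does not settle the matter, because a single-pulse probe still has to be placed over some hemisphere, and sections 3.2.1, 5.1.3 and 10.1.2 describe TEPs by rTMS pulses.
- **The outcome is a change, analysed longitudinally.** This stands for a constant offset with a same-side baseline. It fails without such a baseline, if effects scale with TEP size, or if the two sides respond differently.
- **Treated side is part of the intervention.** Sections 1.2 and 1.3 set out to compare frequency-plus-site packages. That is legitimate, but the side measured need not follow the side treated.

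Three stronger readings are tempting. A reader might infer that two equally effective protocols would be declared different. That depends on an offset or response pattern the documents do not give, and at a 0.5 SD constant offset the rate is 26% on raw values and about 5% on change scores. A reader might infer that the contrast sets a healthy side against a lesioned one, but section 4.1 does not require unilateral CP, so contralesional need not mean unlesioned. A reader might infer that sham is faulty because it pools both sides; the documents instead say that sham delivers no active stimulation, so on the treatment-pulse reading the trouble is the lack of a comparable response.

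**Conclusion.** The point holds as a defect in how a primary outcome is specified. As written, TEPs are tied to rTMS pulses and to the intervention, the active arms are stimulated on opposite hemispheres, sham gives no active stimulation, and no common probed hemisphere is fixed for any assessment. If outcome TEPs are taken at the treated site, the comparison in 2.2.2 cannot be attributed to protocol rather than to hemisphere or pulse rate.

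The size of any error is unknown. The percentages above rest on assumed offsets and responses, normal data, 15 per arm and no dropout. They show that the choice of probed side can matter a great deal or hardly at all, depending on facts the protocol leaves open. The protocol does not state that the wrong comparison will be made; it fails to exclude it, and what is not recorded cannot be repaired at analysis.

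**What to change.** 1. In sections 3.2.1, 5.1.3 and 10.1.2, state that outcome TEPs are evoked by the same single-pulse probe over the same named hemisphere(s) in every CP child, in all three arms, at baseline, post-intervention and follow-up. Probing both sides is preferable; one common side would also serve.
2. In 10.1.2, step f, define the between-arm contrast as baseline-adjusted and within the same hemisphere. If both sides are probed, say which is primary.
3. State that TEPs from treatment pulses are not used for the primary between-arm comparison. They may be described within an arm.
4. Reconcile the side assigned to each frequency in sections 2.1 and 3.1 with section 3.6.4. This review takes no view on which is intended.

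The cost is wording plus, at most, one short extra probe block at each existing assessment. Both hemispheres are already to be mapped and a pre-intervention TMS-EEG is already referred to, so no new visit or device is needed. The downside is a slightly longer session for the child, smaller if only one side is probed.
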